10.1. Periodic evaluation of data

Data will be evaluated half way through and at completion of study by primary investigator

10.2. Data that are reviewed

Data collected on subject forms with comparison to Red Cap data.

10.3. Method of collection of safety information

Safety data will be collected at the time of the procedure by the primary investigator.

10.4. Frequency of data collection

With each procedure and data collection.

10.5. Individuals reviewing the data

The primary investigator as well as study team members.

10.6. Frequency of review of cumulative data

Half way through bronchoscopy data collection and at completion. Safety data will be collected during each procedure.

10.7. Statistical tests

Descriptive statistics will be used for continuous variables, and presented as medians and interquartile ranges. Categorical variables will be expressed as percentages.

10.8. Suspension of research

Will be based on safety data collection following each subject's bronchoscopy.

11. Risks

There is the potential risk of loss of confidentiality with this study due to consent being required however no personal identifiers will be attached to the data we collect. There is no other forseeable risk to the patients involved in this study. All medications and procedures fall within standard treatment and standard of care. The only variable will be the delivery method of the medication used during bronchoscopy. There is no risk to the researchers or hospital staff either. Loss of confidentiality is always a potential risk, but no protected health information will be maintained or collected, minimizing this risk. Risk of randomization is also present however all modalities are considered standard of care.

12. Potential Benefits to Subjects and Others

12.1. Potential Benefits to Subjects

No direct benefit to subjects.

12.2. Potential Benefits to Others

Benefit to society by determining what mode of application of lidocaine prevents severe cough and improves efficiency and decreases potential risks during flexible bronchoscopy and endobronchial ultrasound.

13. Sharing Results with Subjects

Not applicable.

14. Subject Stipend (Compensation) and/or Travel Reimbursements

Not applicable.

15. Economic Burden to Subjects

15.1. Costs

Not applicable.

15.2. Compensation for research-related injury

Not applicable.

16. Resources Available

16.1. Facilities and locations

Pre-anesthesia care unit, floor room or interventional pulmonology clinic where consent process will take place.

Pre-anesthesia care unit where patient will receive dextromethorphan.

Main Procedure Room 1 where lidocaine will be administered and procedure completed. Will collect number of severe coughs, amount of anesthesia, time of procedure and wake up time.

Post-anesthesia care unit where time to discharge readiness, patient cough severity and sore throat severity will be collected.

16.2. Feasibility of recruiting the required number of subjects

There are over 600 combined flexible bronchoscopies performed per year, and include a combination of basic bronchoscopy and EBUS.

16.3. PI Time devoted to conducting the research

The PI will be responsible for oversight of recruitment, oversight of data entry accuracy, and primary data analysis. The PI will also have initial overview to ensure subject safety.

16.4. Availability of medical or psychological resources

Not applicable.

16.5. Process for informing Study Team

The research team currently consists of the principal investigator and four co-investigators. If additional members are added, they will be educated on the confidentiality and data management principles outlined in section 9.

17. Other Approvals

17.1. Other Approvals from External Entities

Not applicable.

17.2. Internal PSU Committee Approvals

Check all that apply: Anatomic Pathology – Hershey only – Research involves the collection of tissues or use of pathologic specimens. Upload a copy of HRP-902 - Human Tissue For Research Form on the "Supporting Documents" page in CATS IRB. This form is available in the CATS IRB Library.
Animal Care and Use – All campuses – Human research involves animals and humans or the use of human tissues in animals
Biosafety – All campuses – Research involves biohazardous materials (human biological specimens in a PSU research lab, biological toxins, carcinogens, infectious agents, recombinant viruses or DNA or gene therapy).
Clinical Laboratories – Hershey only – Collection, processing and/or storage of extra tubes of body fluid specimens for research purposes by the Clinical Laboratories; and/or use of body fluids that had been collected for clinical purposes, but are no longer needed for clinical use. Upload a copy of HRP-901 - Human Body Fluids for Research Form on the "Supporting Documents" page in CATS IRB. This form is available in the CATS IRB Library.
Clinical Research Center (CRC) Advisory Committee— All campuses — Research involves the use of CRC services in any way.

Conflict of Interest Review – All campuses – Research has one or more of study team members indicated as having a financial interest.
Radiation Safety – Hershey only – Research involves research-related radiation procedures. All research involving radiation procedures (standard of care and/or research-related) must upload a copy of HRP-903 - Radiation Review Form on the "Supporting Documents" page in CATS IRB. This form is available in the CATS IRB Library.
IND/IDE Audit – All campuses – Research in which the PSU researcher holds the IND or IDE or intends to hold the IND or IDE.
Scientific Review – Hershey only – All investigator-written research studies requiring review by the convened IRB must provide documentation of scientific review with the IRB submission. The scientific review requirement may be fulfilled by one of the following: (1) external peer-review process; (2) department/institute scientific review committee; or (3) scientific review by the Clinical Research Center Advisory committee. NOTE: Review by the Penn State Hershey Cancer Institute Scientific Review Committee is required if the study involves cancer prevention studies or cancer patients, records and/or
tissues. For more information about this requirement see the IRB website at:
·
http://www.pennstatehershey.org/web/irb/home/resources/investigator

18. Multi-Site Research

18.1. Communication Plans

Not applicable.

18.2. Data Submission and Security Plan

Not applicable.

18.3. Subject Enrollment

Not applicable.

18.4. Reporting of Adverse Events and New Information

Not applicable.

18.5. Audit and Monitoring Plans

Not applicable.

19. Adverse Event Reporting

19.1. Adverse Event Definitions

For drug studies, incorporate the following definitions into the below responses, as written:			
Adverse event	Any untoward medical occurrence associated with the use of the drug in humans, whether or not considered drug related		
Adverse reaction	Any adverse event caused by a drug		

Suspected adverse reaction	Any adverse event for which there is a reasonable possibility that the drug caused the adverse event. Suspected adverse reaction implies a lesser degree of certainty about causality than "adverse reaction". • Reasonable possibility. For the purpose of IND safety reporting, "reasonable possibility" means there is evidence to suggest a causal relationship between the drug and the adverse event.
Serious adverse event or Serious suspected adverse reaction	Serious adverse event or Serious suspected adverse reaction: An adverse event or suspected adverse reaction that in the view of either the investigator or sponsor, it results in any of the following outcomes: Death, a life-threatening adverse event, inpatient hospitalization or prolongation of existing hospitalization, a persistent or significant incapacity or substantial disruption of the ability to conduct normal life functions, or a congenital anomaly/birth defect. Important medical events that may not result in death, be life-threatening, or require hospitalization may be considered serious when, based upon appropriate medical judgment, they may jeopardize the patient or subject and may require medical or surgical intervention to prevent one of the outcomes listed in this definition.
Life-threatening adverse event or life-threatening suspected adverse reaction	An adverse event or suspected adverse reaction is considered "life-threatening" if, in the view of either the Investigator (i.e., the study site principal investigator) or Sponsor, its occurrence places the patient or research subject at immediate risk of death. It does not include an adverse event or suspected adverse reaction that had it occurred in a more severe form, might have caused death.
Unexpected adverse event or Unexpected suspected adverse reaction.	An adverse event or suspected adverse reaction is considered "unexpected" if it is not listed in the investigator brochure, general investigational plan, clinical protocol, or elsewhere in the current IND application; or is not listed at the specificity or severity that has been previously observed and/or specified.

19.2. Recording of Adverse Events

In accordance with applicable policies of The Pennsylvania State University Institutional Review Board (IRB), the investigator will report, to the IRB, any observed or reported harm (adverse event) experienced by a subject or other individual, which in the opinion of the investigator is determined to be (1) unexpected; and (2) probably related to the research procedures. Harms (adverse events) will be submitted to the IRB in accordance with the IRB policies and procedures.

19.3. Causality and Severity Assessments

The investigator will promptly review documented adverse events and abnormal test findings to determine 1) if the abnormal test finding should be classified as an adverse event; 2) if there is a reasonable possibility that the adverse event was caused by the study drug(s) or device(s); and 3) if the adverse event meets the criteria for a serious adverse event.

If the investigator's final determination of causality is "unknown and of questionable relationship to the study drug(s) or device(s)", the adverse event will be classified as associated with the use of the study drug(s) or device(s) for reporting purposes. If the investigator's final determination of causality is "unknown but not related to the study drug(s) or device(s)", this determination and the rationale for the determination will be documented in the respective subject's case history.

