1.3. Secondary Study Endpoints

Secondary endpoints will include: additional amount(s) of fentanyl and propofol used to suppress cough during procedure, cough and sore throat post-procedure and time to emergence following the end of the procedure.

2. Background

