2.3. Study Rationale

While the procedures of flexible bronchoscopy and endobronchial ultrasound is commonly performed to assess a wide range of lung disease, studies evaluating the mode of administration of topical lidocaine to prevent coughing and improve efficiency of the procedure have not yet been completed. We propose a prospective, randomized, stratified sampling, open label study of topical vs nebulized vs atomized lidocaine during flexible bronchoscopy and endobronchial ultrasound. Postoperative outcome assessors will be blinded to intraoperative therapy. We propose to evaluate the different modes of administration of topical lidocaine and their effect on the number of severe coughs as per anesthesia and the bronchoscopist, total dosing of anesthesia, post-procedure cough and sore throat and complications related to lidocaine.

As there have been no studies in regards to the mode of lidocaine application in bronchoscopy, our study is a feasability study to identify if a difference is present between nebulized and topical groups. If one is identified, we will plan to determine number needed to power a future superiority study.

Inclusion and Exclusion Criteria

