7.4.5. Blinding of the Test Article

Mode of administration will not be blinded to anesthesiologist or bronchoscopist.

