19.5. Reporting Adverse Reactions and Unanticipated Problems to the Responsible IRB

In accordance with applicable policies of The Pennsylvania State University Institutional Review Board (IRB), the investigator will report, to the IRB, any observed or reported harm (adverse event) experienced by a subject or other individual, which in the opinion of the investigator is determined to be (1) unexpected; and (2) probably related to the research procedures. Harms (adverse events) will be submitted to the IRB in accordance with the IRB policies and procedures.

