20.1.2. Safety Monitoring

Adverse events will be identified and recorded on each subject form by the monitor and will be reviewed by the primary investigator who is present during all procedures.

The **Principal Investigator** will confirm that all adverse events (AE) are correctly entered into the AE case report forms by the coordinator; be available to answer any questions that the coordinators may have concerning AEs; and will notify the IRB and/or DSMB of all applicable AEs as appropriate. All assessments of AEs will be made by a licensed medical professional who is an investigator on the research.

21. Future Undetermined Research: Data and Specimen Banking

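### Lidocaine-related complications are undefined and the only relatedness procedure is an arm-aware investigator's judgement; tabulate all recorded adverse events by arm, and reconcile the causality and IRB reporting rules

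*Combined protocol and SAP*

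**What the plan says.** Section 2.3 (Study Rationale) lists what the modes will be evaluated on, ending with "post-procedure cough and sore throat and complications related to lidocaine". This is the only place where lidocaine complications appear as an outcome. The secondary endpoints in section 1.3 are extra fentanyl and propofol, then "cough and sore throat post-procedure and time to emergence following the end of the procedure"; complications are not among them. Section 8.3 plans descriptive statistics only.

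On causality, section 19.3 has the investigator decide "if there is a reasonable possibility that the adverse event was caused by the study drug(s) or device(s". Where the investigator's final view is that the cause is unknown and the relationship doubtful, "the adverse event will be classified as associated with the use of the study drug(s) or device(s) for reporting purposes". Section 20.1.2 adds: "All assessments of AEs will be made by a licensed medical professional who is an investigator on the research". It also says that the primary investigator reviews the recorded events and is present at all procedures.

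On blinding, section 7.4.5 states: "Mode of administration will not be blinded to anesthesiologist or bronchoscopist". Section 19.6 likewise says that modes are not blinded. Section 2.3 blinds the postoperative outcome assessors, but nothing gives them a part in judging causality.

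On reporting, sections 19.2 and 19.5 both send a harm to the IRB if the investigator considers it "unexpected; and (2) probably related to the research procedures". Sections 19.4.1 and 19.4.2, on reports to the FDA, are marked as not applicable.

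**The concern.** There are two separate matters.

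The first is bias in a comparison. Patients receive propofol, fentanyl, alfentanil, a laryngeal mask and a bronchoscope as well as lidocaine, so the cause of an intraoperative event will often be open to judgement. If an event counts as a lidocaine complication only after someone who knows the mode has judged it related, the complication percentages reflect attribution as well as event rates. A difference between modes could then appear where none exists, or a real one could be hidden.

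The second is a mismatch of rules. Section 19.3 treats doubtful events as associated for the purpose of reporting, yet the explicit IRB trigger in sections 19.2 and 19.5 asks for more than that. A reader cannot tell whether a doubtful event is to be sent to the IRB.

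**Working it through.** The plan gives no figure that depends on this point. Section 8.2 marks sample size determination as not applicable, so there is no error rate, power or effect size to reproduce. The check is a reading of the text, followed by an illustration on assumed rates.

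**Who decides relatedness**

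1. Section 2.3 names the outcome without a list or criterion. Sections 1.2, 1.3 and 8.3 do not mention it, nor do the data items in 7.1 and 16.1.
2. The only relatedness procedure in the protocol is section 19.3, carried out by an investigator (20.1.2).
3. The primary investigator collects the safety data at the procedure (10.3), reviews events and attends all procedures (20.1.2). With modes unblinded (7.4.5, 19.6), that person will know the arm.
4. No blinded or independent assessment of causality is described.

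**What unequal attribution would do**

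Let *p* be the true proportion of patients with an event, the same under every mode, and *a* the probability that the assessor ascribes the event to lidocaine. Then:

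apparent related rate = *p* × *a*; apparent ratio, nebulized to topical = *a*(neb) / *a*(top)

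So *p* cancels from the ratio. All rates below are assumptions; the documents give none.

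| *p* | *a*(top) | *a*(neb) | Topical | Nebulized | Ratio |
|---|---|---|---|---|---|
| 20% | 50% | 50% | 10% | 10% | 1.0 |
| 20% | 50% | 75% | 10% | 15% | 1.5 |
| 20% | 40% | 80% | 8% | 16% | 2.0 |
| 20% | 30% | 90% | 6% | 18% | 3.0 |
| 20% | 80% | 40% | 16% | 8% | 0.5 |

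At *p* = 10% and 30% the 40% versus 80% row becomes 4% versus 8% and 12% versus 24%, with the ratio still 2.0. The last row shows that the direction is not fixed. A true difference can also be masked: 10% × 80% = 8% and 20% × 40% = 8%. A count of all recorded events would show equality in every row of the table, and the true 10% versus 20% in the masking example, provided that events are recognised and recorded equally in each arm.

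**Precision**

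Section 8.1 plans 24 topical, 12 jet nebulizer and 12 vibrating mesh patients (24 + 12 + 12 = 48). One reclassified patient moves an arm by 1/24 = 4.2 or 1/12 = 8.3 percentage points. With no events at all, the one-sided 95% upper limit, 1 − 0.05^(1/n), is 11.7% for n = 24 and 22.1% for n = 12. This imprecision affects any binary outcome here and would remain without bias.

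**Following a doubtful event through the reporting text**

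- Section 19.1: it is an adverse event whether or not it is thought to be drug related.
- Section 20.1.2: it is recorded on the subject form.
- Section 19.3: it is classed as associated with the study drug or device, expressly for reporting.
- Sections 19.2 and 19.5: it does not meet the probably-related condition, and it would also have to be unexpected. These sections refer to research procedures, not to the drug or device.
- Section 19.4: no FDA route.
- Section 20.1.2: the principal investigator notifies the IRB and/or a DSMB of applicable events, a term that is not defined.

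The event is therefore kept in the study data, but whether it goes to the IRB is not settled.

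**The case against.** The strongest reply is that section 2.3 never refers to section 19.3, nor the reverse. The phrase in 2.3 could mean a list of recognised lidocaine complications, counted without any causality judgement. That is fair: a reader might infer that lidocaine complications are by definition the events judged related under 19.3, and the documents do not say so. What stands is that no such list is given and no other relatedness procedure exists, so the outcome is open to exactly this use.

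Second, the stakes are limited. Complications are not a listed endpoint, the study is a 48-patient feasibility study, and the analysis is descriptive. This stands. It bounds the consequence to a secondary safety description, but percentages by arm carry attribution bias whether or not they are tested.

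Third, a reader might infer that doubtful events go unreported or that sections 19.2 and 19.5 cancel the safeguard in 19.3. The documents do not support that. The events stay on the study forms, 20.1.2 gives a route to the IRB or DSMB (though a vague one), and 19.2 and 19.5 defer to IRB policies that are not in the documents. Classification and an IRB trigger may also legitimately use different thresholds. What stands is that 19.3 ties its classification to reporting, and the text does not say to which reporting.

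Fourth, a table of all adverse events mixes anesthetic and bronchoscopic events with those due to lidocaine and could dilute a real signal. This is a true cost. Tabulating by event type and keeping the related events as a second listing reduces it.

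**Conclusion.** The concern holds in a conditional form. If relatedness is decided by the only procedure in the protocol, an investigator's judgement made with knowledge of the arm, the descriptive comparison of lidocaine complications can be distorted by attribution that differs by arm. The blinded postoperative assessors do not remove this, because nothing links them to causality.

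The size is unknown. It is nil under equal attribution; the ratios of 0.5 to 3.0 shown rest wholly on assumed attribution probabilities and are not a forecast. A reader might take a twofold spurious difference as the expected result, but nothing in the documents supports any particular value or direction.

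The mismatch between 19.3 and 19.2/19.5 is a real ambiguity about what is sent to the IRB. It is not evidence that events are lost from the study.

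**What to change.** 1. In sections 2.3 and 8.3, state that the safety comparison is the number and percentage of patients per arm with any adverse event recorded on the subject form, regardless of attribution, broken down by event type. List events judged related to lidocaine second. If the sponsor has particular lidocaine complications in mind, name them in 2.3.
2. Reconcile sections 19.2, 19.3, 19.5 and 20.1.2 with each other and with the IRB's own policy. State what the reporting in 19.3 refers to, which events 20.1.2 treats as applicable, and whether an event of doubtful cause goes to the IRB. The condition that an event be unexpected needs to be covered too, since altering only the probably-related condition would leave it in force.

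The cost is wording only, because adverse events are already recorded on each subject form. The small downside is that unrelated anesthetic and procedural events will appear in the table. The change also does not remove arm-aware recognition of events: staff who know the mode still decide what to record, and the report should say so.

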19.4. Reporting of Adverse Reactions and Unanticipated Problems to the FDA

19.4.1. Written IND/IDE Safety Reports

Not applicable as new drug is not being studied, only comparison of mode of application.

19.4.2. Telephoned IND Safety Reports – Fatal or Life-threatening Suspected Adverse Reactions

Not applicable as new drug is not being studied, only comparison of mode of application

19.5. Reporting Adverse Reactions and Unanticipated Problems to the Responsible IRB

In accordance with applicable policies of The Pennsylvania State University Institutional Review Board (IRB), the investigator will report, to the IRB, any observed or reported harm (adverse event) experienced by a subject or other individual, which in the opinion of the investigator is determined to be (1) unexpected; and (2) probably related to the research procedures. Harms (adverse events) will be submitted to the IRB in accordance with the IRB policies and procedures.

19.6. Unblinding Procedures

Modes of administration are not blinded.

